9.1.2 Safety

There are no primary objectives for safety.

9.1.3 Efficacy

No clinical efficacy data will be collected in this trial.

9.2 Secondary Endpoints and Assessment Methods

9.2.1 Immunogenicity

9.2.1.1 Immunogenicity Endpoints

The secondary endpoints for the evaluation of immunogenicity are:

STAGE I:

- Neutralizing Ab titers against each dengue virus serotype 28 days post-Injection 2 in Group 1, 28 days post-Injection 3, and 1 year post-injection 3 in all 3 groups

STAGE II:

- Neutralizing Ab titers against each dengue virus serotype 28 days post-Injection 3 in Group 1, immediately prior to booster injection and 28 days post-booster injection in all 3 groups
- Seroconversion rates 28 days after injection for each of the 4 parental dengue virus strains of CYD dengue vaccine: percentages of subjects with either a pre-booster titer < 10 (1/dil) and a post-booster titer ≥ 40 (1/dil), or a pre-booster titer ≥ 10 (1/dil) and a ≥ 4 -fold increase in post-booster titer as determined immediately prior to and 28 days post-booster in all 3 groups.

9.2.1.2 Immunogenicity Assessment Methods

The immunogenicity assessment methods for the secondary immunogenicity endpoints are the same as those presented in Section 9.1.1.2.

For each particular immunogenicity endpoint, the assay will be performed on the blood samples taken at:

STAGE I Endpoints:

- 28 days post-Injection 2 (Group 1), and 28 days post-Injection 3 (all groups)

STAGE II Endpoints:

- Immediately prior to and 28 days post-booster injection in all 3 groups

9.2.2 Safety

9.2.2.1 Safety Definitions

The following definitions are taken from the ICH E2A Guideline for Clinical Safety Data Management: Definitions and Standards for Expedited Reporting.

Adverse Event (AE):

An AE is any untoward medical occurrence in a patient or clinical investigation subject administered a pharmaceutical product and which does not necessarily have to have a causal relationship with this treatment. An AE can therefore be any unfavorable and unintended sign (including an abnormal laboratory finding, for example), symptom or disease temporally associated with the use of a medicinal product, whether or not considered related to the medicinal product.

Therefore an AE may be:

- A new illness
- The worsening of a concomitant illness
- An effect of the vaccination, including the comparator
- A combination of the above

All AEs include serious and non-serious AEs.

Surgical procedures are not AEs; they are the action taken to treat a medical condition. It is the condition leading to the action taken that is the AE (if it occurs during the trial period).

Pre-existing medical conditions are not to be reported as AEs. However, if a pre-existing condition worsens in frequency or intensity, or if in the assessment of the treating physician there is a change in its clinical significance, this change should be reported as an AE (exacerbation). This applies equally to recurring episodes of pre-existing conditions (eg, asthma) if the frequency or intensity increases post-injection.

Serious Adverse Event (SAE):

Serious and *severe* are not synonymous. The term *severe* is often used to describe the intensity of a specific event as corresponding to Grade 3. This is not the same as *serious* which is based on patient / event outcome or action criteria usually associated with events that pose a threat to a patient's life or functioning. Seriousness, not severity, serves as a guide for defining regulatory reporting obligations.

An SAE is any untoward medical occurrence that at any dose

- Results in death
- Is life-threatening^a
- Requires inpatient hospitalization or prolongation of existing hospitalization^b
- Results in persistent or significant disability / incapacity^c
- Is a congenital anomaly / birth defect
- Is an important medical event^d

Additionally, the following important medical events are to be considered as SAEs and reported to the Sponsor according to the procedure described in [Section 10](#):

- Serious AESIs

^a The term "life-threatening" refers to an event in which the subject was at risk of death at the time of the event; it does not refer to an event which hypothetically might have caused death if it were more severe.

^b All medical events leading to hospitalizations will be recorded and reported as SAEs, with the exception of: hospitalization planned before inclusion into the study or out-patient treatment with no hospitalization.

^c "Persistent or significant disability or incapacity" means that there is a substantial disruption of a person's ability to carry out normal life functions.

^d Medical and scientific judgment should be exercised in deciding whether expedited reporting is appropriate in other situations, such as important medical events that may not be immediately life-threatening or result in death or hospitalization but may jeopardize the health of the subject or may require intervention to prevent one of the other outcomes listed in the definition above. These should also usually be considered serious. Examples of such events include allergic bronchospasm requiring intensive treatment in an emergency room or at home, blood dyscrasias or convulsions that do not result in inpatient hospitalization, or the development of drug dependency or drug abuse, new onset diabetes, or autoimmune disease.

Adverse Reaction (AR):

All noxious and unintended responses to a medicinal product related to any dose should be considered AR.

(The phrase “responses to a medicinal product” means that a causal relationship between a medicinal product and an AE is at least a reasonable possibility)

Unexpected Adverse Reaction:

An unexpected adverse reaction is an AR, the nature or severity of which is not consistent with the applicable product information (eg, Investigator’s Brochure for an unapproved investigational medicinal product).

The following additional definitions are used by Sanofi Pasteur:

Solicited Reaction:

A solicited reaction is an event that is prelisted in the eCRF. The assessment of these AEs post-vaccination is mandatory. A solicited reaction is defined by a combination of:

- Symptom and
- Onset post-vaccination

eg, injection site pain between D0 and D7 post-vaccination, or headache between D0 and D14.

A solicited reaction is therefore an AR observed and reported under the conditions (symptom and onset) prelisted (ie, solicited) in the eCRF and considered as related to vaccination.

Unsolicited AE / AR:

An unsolicited AE is an observed AE that does not fulfill the conditions prelisted in the eCRF in terms of diagnosis and / or onset post-vaccination, ie, excluding solicited reactions, eg, if headache between D0 and D14 is a solicited reaction (ie, prelisted in the eCRF), then a headache starting on D14 is a solicited reaction, whereas headache starting on D15 post-vaccination is an unsolicited AE.

An unsolicited non-serious AE is an unsolicited AE excluding SAEs.

Injection Site Reaction:

An injection site reaction^a is an AR at and around the injection site. Injection site reactions are commonly inflammatory reactions.

^a All injection site AEs are considered to be related to vaccination and are therefore all *injection site reactions*.

Systemic AE:

Systemic AEs are all AEs that are not injection site reactions. They therefore include systemic manifestations such as headache, fever, as well as localized or topical manifestations that are not associated with the vaccination site, eg, erythema that is localized but that is not at the injection site.

Adverse Events of Special Interest (AESIs):

AEs of special interest are AEs that are considered by the Sponsor to be relevant for the monitoring of the safety profile of the investigational vaccine.

9.2.2.2 Safety Endpoints

The primary endpoints for the evaluation of safety are:

STAGE I and STAGE II

- Occurrence, nature (Medical Dictionary for Regulatory Activities [MedDRA] preferred term), duration, intensity, action taken, whether it leads to discontinuation or not, and relationship to vaccination of any AEs reported in the 30 minutes after injection.
- Occurrence, time to onset, number of days of occurrence, intensity, whether it leads to discontinuation or not, and action taken of solicited (prelisted in the subject's diary card and electronic case report form [eCRF]) injection site reactions (pain, erythema, and swelling) occurring up to 7 days after injection.
- Occurrence, time to onset, number of days of occurrence, intensity, whether it leads to discontinuation or not, and action taken of solicited systemic reactions (fever, headache, malaise, myalgia, and asthenia) occurring up to 14 days after vaccination.
- Occurrence, nature (MedDRA preferred term), time to onset, duration, intensity, whether it leads to discontinuation or not, action taken and relationship to vaccination (for systemic AEs only) of up to 28 days after injection.
- Occurrence, nature (MedDRA preferred term), time to onset, duration, intensity, action taken, and relationship to vaccination of non-serious AESIs occurring up to 7 days after injection.
- Occurrence of SAEs, including serious AESIs (with specific time windows according to the nature of the event) throughout the trial).
- Occurrence of hospitalized VCD cases throughout the trial (ie, from D0 through end of study).

9.2.2.3 Safety Assessment Methods

At V01, V03, V04, V05, V06, V07 and V10 (and also V08 and V09 for subjects in the AIT subset), the Investigator or an observer-blind delegate will perform a clinical or medically-driven physical examination, and will ask the subject / or parent or / legally acceptable representative about any solicited reactions and unsolicited AEs recorded in the DC or MA, as well as about any other AEs that may have occurred since the previous visit. All relevant data will be transcribed into the eCRF according to the instructions provided by the Sponsor.

9.2.2.3.1 Immediate Post-vaccination Surveillance Period

Subjects will be kept under observation for 30 minutes after injection to ensure their safety. The post-injection surveillance should be documented in the source document. Any AE that occurs during this period will be noted on the source document and recorded in the eCRF, as follows:

- Any unsolicited systemic AE occurring during the first 30 minutes post-injection will be recorded on the eCRF as immediate unsolicited systemic AE.
- Solicited and unsolicited injection site reactions and solicited systemic reactions will be recorded and analyzed as starting on the day of vaccination.
- Any SAE occurring during the first 30 minutes post-injection will be reported in the same way as any other SAE and to the Sponsor, according to the procedures described in [Section 10](#).

9.2.2.3.2 Reactogenicity (Solicited Reactions From Day 0 to Day 7 After Vaccination)

After injection, subjects / subjects' parents / legally acceptable representatives will be provided with a safety DC, a MA, a digital thermometer, and a flexible ruler, and will be instructed how to use them. The following items will be recorded by the subjects / subjects' parents / legally acceptable representatives in the DC on the day of vaccination and for the next 7 days (ie, D0 to D7) for the solicited injection site reactions and for the next 14 days (ie, D0 to D14) for the solicited systemic reactions, until resolution:

- Daily temperature, with the route by which it was taken
- Daily measurement or intensity grade of all other solicited injection site and systemic reactions
- Action taken for each event, if any (eg, medication)

The action taken by the subjects / subjects' parents / legally acceptable representatives to treat any **solicited reactions** will be classified in the eCRF using the following scale:

- 0: None
- 1: Medication (self-medication with an existing prescription or over-the-counter medication)
- 2: Health care provider contact (no new medication prescribed)
- 3: Health care provider contact and prescription of a new medication (health care provider instructed subject to take a new medication, either an over-the-counter medication or one requiring a written prescription)
- 4: Hospitalization (inpatient)

Subjects / subjects' parents / legally acceptable representatives will be contacted by telephone 2, 4, 8, 10, 14, 16, 18, 20, and 22 months after the vaccination to remind them to record all safety information in the DC.

If the timing of the telephone call should fall on a weekend or a holiday, the call should be made on the next business day. If contact is not made on the designated day, study staff will continue calling until contact is made. Every telephone attempt and its outcome will be documented in the source document.

Table 9.1 and Table 9.2 present, respectively, the injection site reactions and systemic reactions that are prelisted in the DCs and eCRF, together with the intensity scales.

Table 9.1: Solicited injection site reactions: terminology, definitions, and intensity scales for trials involving children, adolescents and adults

eCRF term (MedDRA lowest level term [LLT])	Injection site pain	Injection site erythema	Injection site swelling
Diary card term	Pain	Redness	Swelling
Definition		Presence of a redness including the approximate point of needle entry	Swelling at or near the injection site Swelling or edema is caused by a fluid infiltration in tissue or cavity and, depending on the space available for the fluid to disperse, swelling may be either soft (typically) or firm (less typical) to touch and thus can be best described by looking at the size of the swelling
Intensity scale* †	Grade 1: Easily tolerated Grade 2: Sufficiently discomforting to interfere with normal behavior or activities Grade 3: Incapacitating, unable to perform usual activities	Grade 1: > 0 to < 25 mm Grade 2: ≥ 25 to < 50 mm Grade 3: ≥ 50 mm	Grade 1: > 0 to < 25 mm Grade 2: ≥ 25 to < 50 mm Grade 3: ≥ 50 mm
Intensity scale ‡	Grade 1: No interference with activity Grade 2: Some interference with activity Grade 3: Significant; prevents daily activity	Grade 1: ≥ 25 to ≤ 50 mm Grade 2: ≥ 51 to ≤ 100 mm Grade 3: > 100 mm	Grade 1: ≥ 25 to ≤ 50 mm Grade 2: ≥ 51 to ≤ 100 mm Grade 3: > 100 mm

* For the subjective reaction of pain, subjects / parents / legally acceptable representatives will record the intensity level (Grade 1, 2, or 3) in the diary card. For the measurable reactions of redness and swelling, they will record just the size of the reaction, and the classification as Grade 1, 2, or 3 will be assigned at the time of the statistical analysis

† Intensity scale for children aged 9 to 11 years

‡ Intensity scale for adolescents and adults ≥ 12 years of age

Table 9.2: Solicited systemic reactions: terminology, definitions, and intensity scales

eCRF term (MedDRA lowest level term [LLT])	Fever	Headache	Malaise	Myalgia	Asthenia
Diary card term	Temperature	Headache	Feeling unwell	Muscle aches and pains	Weakness
Definition	Elevation of temperature to $\geq 38.0^{\circ}\text{C}$	Pain or discomfort in the head or scalp. Does not include migraine.	General ill feeling. Malaise is a generalized feeling of discomfort, illness, or lack of well-being that can be associated with a disease state. It can be accompanied by a sensation of exhaustion or inadequate energy to accomplish usual activities.	Muscle aches and pains are common and can involve more than one muscle at the same time. Muscle pain can also involve the soft tissues that surround muscles. These structures, which are often referred to as connective tissues, include ligaments, tendons, and fascia (thick bands of tendons). Does not apply to muscle pain at the injection site which should be reported as injection site pain.	Generalized weakness.
Intensity scale*	Grade 1: $\geq 38.0^{\circ}\text{C}$ to $\leq 38.4^{\circ}\text{C}$ Grade 2: $\geq 38.5^{\circ}\text{C}$ to $\leq 38.9^{\circ}\text{C}$ Grade 3: $\geq 39.0^{\circ}\text{C}$	Grade 1: No interference with activity Grade 2: Some interference with activity Grade 3: Significant; prevents daily activity	Grade 1: No interference with activity Grade 2: Some interference with activity Grade 3: Significant; prevents daily activity	Grade 1: No interference with activity Grade 2: Some interference with activity Grade 3: Significant; prevents daily activity	Grade 1: No interference with activity Grade 2: Some interference with activity. Grade 3: Significant; prevents daily activity

* For all reactions but fever, subjects or parents / legally acceptable representatives will record the intensity level (Grade 1, 2, or 3) in the diary card. For fever, they will record the body temperature, and the classification as Grade 1, 2, or 3 will be assigned at the time of the statistical analysis.

Important notes for the accurate assessment of temperature:

Subjects / Parents / Legally acceptable representatives are to measure body temperature once per day, preferably always at the same time. The optimal time for measurement is the evening, when body temperature is the highest. Temperature is also to be measured at the time of any apparent fever. The observed daily temperature and the route of measurement are to be recorded in the DC, and the highest temperature will be recorded by the site in the eCRF. The preferred route for this trial is axillary. Pre-vaccination temperature is also systematically collected by the Investigator on the source document for all subjects. Tympanic thermometers must not be used.

9.2.2.3.3 Unsolicited Non-serious Adverse Events From Day 0 to Day 28 After Each Vaccination

In addition to recording solicited reactions, subjects / subjects' parents / legally acceptable representatives will be instructed to record any other medical events that may occur during the 28-day period after injection. Space will be provided in the DC for this purpose.

For each unsolicited non-serious AE, the following information is to be recorded:

- Start and stop dates^a
- Intensity of the event:
 - For measurable unsolicited non-serious AEs that are part of the list of solicited reactions, the size of the AE as well as the temperature for fever will be collected and analyzed based on the corresponding scale used for solicited reactions (see [Table 9.1](#) and [Table 9.2](#))
 - Other unsolicited non-serious AEs will be classified according to the following intensity scale:
 - Grade 1: No interference with activity
 - Grade 2: Some interference with activity
 - Grade 3: Significant; prevents daily activity
- Action taken for each AE, if any (eg, medication)

The action taken by the subject / subjects' parent / legally acceptable representative to treat any **unsolicited AEs** will be classified in the eCRF using the following scale:

- 0: None
- 1: Medication (self-medication with an existing prescription or over-the-counter medication)
- 2: Health care provider contact (no new medication prescribed)

^a The stop date of all related AEs will be actively solicited. For other events, the investigator will provide the stop date when it becomes available. AEs for which no stop date was obtained during the course of the trial will be considered as ongoing at the end of the trial.

3: Health care provider contact and prescription of a new medication (health care provider instructed subject to take a new medication, either an over-the-counter medication or one requiring a written prescription)

- Whether the AE led to discontinuation

Whether the AE was related to vaccination (for unsolicited systemic AEs). See [Section 9.2.2.3.6](#) for the assessment of causality.

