4.4.2.1.6 Overall Number of Days of Occurrence

If a reaction is ongoing at the end of the solicited period, then the overall number of days of occurrence is derived from the daily intensities and the stop date of the reaction after the end of the solicited period. The overall number of days of occurrence is:

- $(\text{stop date} - \text{last vaccination date}) + (\text{number of days of occurrence within the solicited period}) - \text{length of the solicited period} + 1$

If the stop date is missing or incomplete (contains missing data [MD]), the overall number of days of occurrence will be considered as Missing.

Overall number of days of occurrence will be displayed by category (range) as follows:

- Injection site reactions (D0-D7): 1-3 days, 4-7 days, ≥ 8 days, missing
- Systemic reactions (D0-D14): 1-3 days, 4-7 days, 8-14 days, ≥ 15 days, missing

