4.4.2.2.5 Duration

Duration is derived from the start and stop dates of the unsolicited non-serious AE provided in the clinical database:

- Stop date of unsolicited non-serious AE - start date of unsolicited non-serious AE + 1.

The duration should be considered as missing only if one or both of the start and stop dates of the unsolicited non-serious AE is missing or partially missing.

Duration will be displayed by period as follows: 1-3 days, 4-7 days, 8-14 days, 15 days or more, Missing.

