4.4.2.3.3 Duration

Duration will be computed using the same methodology than for unsolicited non-serious AEs described in [Section 4.4.2.2.5](#).

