5.3.2.5 Start Date and Stop Date

Missing or partially missing start dates for unsolicited AEs will remain missing and not be imputed. If either the start or stop date is missing or partially missing, the time to onset will be considered to be missing. Nevertheless unsolicited AEs with missing time to onset will be included in analyses according to the visit collected.

Missing or partially missing stop dates for AEs (solicited reactions and unsolicited AEs) will remain missing and not be imputed.

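### The SAP's missing-stop-date rules code some solicited reactions as missing although they are already known to be in the longest duration category, and leave persistent unsolicited AEs unidentifiable

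*Protocol*

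**What the plan says.** **Solicited reactions.** Three SAP derivations bear on this.

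- SAP 4.4.2.1.5 counts graded days within the solicited period from the daily intensities alone. Its top categories are 8 days (injection site) and 15 days (systemic).
- SAP 4.4.2.1.7 derives ongoing status from intensities, not from the investigator's flag. The reaction must be at least Grade 1 on the last solicited day and at least Grade 1 afterwards.
- SAP 4.4.2.1.6 extends the count of an ongoing reaction to its stop date, with top categories of ≥8 and ≥15 days. If the stop date is missing or incomplete, "the overall number of days of occurrence will be considered as Missing".

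**Unsolicited AEs.** The footnote on start and stop dates in Protocol 9.2.2.3.3 says "The stop date of all related AEs will be actively solicited". For other events the investigator supplies the date when it becomes available. It then adds: "AEs for which no stop date was obtained during the course of the trial will be considered as ongoing" when the trial ends. SAP 4.4.2.2.5 computes duration as stop minus start plus 1 and says: "The duration should be considered as missing only if one or both of the start and stop dates" are wholly or partly absent. It displays 1-3, 4-7, 8-14, 15 or more, and Missing. SAP 5.3.2.5 repeats that missing or partial stop dates "will remain missing and not be imputed". Protocol 12.3.2 says that no safety data will be replaced and leaves the details to the SAP.

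**The concern.** A duration can be unknown in its exact value and still be known to exceed a category boundary. The solicited rule discards that knowledge, so one reaction can appear in the top category of one table and as missing in a companion table.

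For unsolicited AEs, the protocol gives records with no stop date a meaning, ongoing, that the SAP never uses. A confirmed persistent event and an event whose end date was merely not written down in full then look the same. A reader checking whether the vaccine produces long-lasting events cannot separate the two. Duration of unsolicited AEs is a listed safety endpoint (Protocol 9.2.2.2), so the tables should be able to answer that question.

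**Working it through.** The plan states no figure to reproduce. The check applies the SAP's own formulas.

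**1. Solicited reactions: the minimum that is already known**

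Let k be the graded days within the solicited period. Ongoing status requires a graded reaction after the period, hence at least one further day:

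minimum overall days = k + 1

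| Reaction | Period length | k if graded every day | Minimum | Top category, SAP 4.4.2.1.6 | Category, SAP 4.4.2.1.5 |
|---|---|---|---|---|---|
| Injection site, D0-D7 | 8 days | 8 | 8 + 1 = 9 | ≥8 | 8 days |
| Systemic, D0-D14 | 15 days | 15 | 15 + 1 = 16 | ≥15 | 15 days |

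The SAP 4.4.2.1.6 formula agrees. It is (stop date − vaccination date) + k − period length + 1. With the earliest possible stop after the period:

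- Injection site, stop on D8: 8 + 8 − 8 + 1 = 9.
- Systemic, stop on D15: 15 + 15 − 15 + 1 = 16.

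A later stop only adds days. The top category is therefore certain without the stop date, yet the rule assigns Missing. The category is also certain at k = 7 (7 + 1 = 8) and k = 14 (14 + 1 = 15) for an ongoing reaction. Below those values it is not, and Missing is the right entry.

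**2. Unsolicited non-serious AEs: what the protocol convention implies**

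Analysed onset is D0-D28 (SAP 4.4.2.2.4). The study ends 6 months after the Year 2 booster (SAP 5.4), taken here as about 182 days. The latest onset gives the shortest duration:

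- Ongoing at booster + 6 months: 182 − 28 + 1 = 155 days, always 15 or more.
- Last seen at V10, 28 to 42 days after booster: 28 − 28 + 1 = 1 day up to 42 − 28 + 1 = 15 days, so not always 15 or more.

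The placement thus depends on whether the event was really observed to be ongoing, and until when. The convention alone does not show that.

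**3. Size of the unsolicited effect**

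The 15-days-or-more share can rise by at most the share of AEs with a known start date and no stop date. The documents do not give that share. If it were 1% to 10% (assumption), the ceiling would be 1 to 10 percentage points. The actual shift would be smaller to the extent that such events had resolved on an unrecorded date.

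**The case against.** **No contradiction.** The footnote assigns a status and gives no duration rule or censoring date. Protocol 12.3.2 rules out replacement and defers to the SAP. This stands: the unsolicited part is a convention left unapplied, not a breach of the protocol, and SAP 5.7 had no clear departure to list. Assigning a category that known data already guarantee is not replacement, however, so Protocol 12.3.2 does not rescue the solicited rule.

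**The listed solicited endpoint is safe.** Protocol 9.2.2.2 lists number of days of occurrence, which SAP 4.4.2.1.5 derives without a stop date. This also stands, and it confines the fault to the overall-days table. That table still carries a wrong category.

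**Nothing disappears.** Missing is a displayed category, so its count is visible. True, but the count mixes ongoing events with partial and unknown dates.

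**A reader might infer that the longest events are lost and the tables are biased toward short ones.** The documents do not support this. Stop dates are actively sought only for related AEs, so a short unrelated AE can lack one. Subjects lost to follow-up are not pursued further (Protocol 5.2.11). Related AEs unresolved at the end of participation are followed until they resolve, stabilise or become chronic (Protocol 5.1.4). The mix of events without a stop date is therefore unknown.

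**A reader might extend the point to SAEs.** SAP 4.4.2.3.3 does say "Duration will be computed using the same methodology than for unsolicited non-serious AEs". But the planned SAE description in SAP 5.1.2.2.2.2 omits duration, outcome is summarised as collected (SAP 4.4.2.4.4), and the footnote sits in the section on non-serious AEs. An SAE that starts in the last 14 days of follow-up and is still ongoing has lasted under 15 days. This is not a main point.

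**Conclusion.** The point holds in two parts of different strength.

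- **Solicited reactions (firm).** For an ongoing reaction graded on every solicited day, SAP 4.4.2.1.6 gives Missing where ≥8 or ≥15 days is certain. This rests only on the SAP's own definition of ongoing. How many reactions are affected is not stated.
- **Unsolicited AEs (a gap).** The SAP never carries the protocol's ongoing convention into analysis, so persistent events cannot be told apart from incomplete dates. The 15-days-or-more share can be understated, but the documents give no basis for a size or a ratio.

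The effect is limited to descriptive safety tables. No hypothesis test, primary endpoint or occurrence count changes.

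**What to change.** - **SAP 4.4.2.1.6.** When the reaction is ongoing and the stop date is missing or incomplete, take days of occurrence within the solicited period + 1 as the minimum. Assign the top category when the minimum reaches it; otherwise keep missing.
- **SAP 4.4.2.2.5.** Show ongoing / no stop date obtained as its own category, separate from partial or unknown dates. Where the investigator confirms that the event is ongoing at last contact, report the minimum duration: last contact date − start date + 1. Do not move an event into 15 days or more merely because no stop date was obtained.
- **SAP 5.3.2.5.** Cross-refer to these two rules, so that the statement on stop dates is not read as overriding them.

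The cost is SAP wording, one extra table category and a few lines of derivation code. Stop dates themselves remain unimputed, in keeping with Protocol 12.3.2.
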